#### **Summary statistics at scheduled visits**

Summary statistics (for Screening value, Baseline value, observed values, and observed changes from Baseline) at scheduled visits will be provided by treatment group for HbA1c value over the treatment period. The last on-treatment value will be presented in a separate row. The summary will include the number of observations, mean, SD, SE, minimum, median, and maximum. Graphical presentations will also be used to examine trends over time using mean values (±SE) and mean changes from Baseline (±SE) at each of the scheduled visits (using OC).

#### **2.4.4.2 Analyses of secondary efficacy endpoints**

For secondary efficacy endpoints included in the multiplicity procedure described in [Section 2.4.4.3](#), 2-sided statistical tests for the superiority of efpeglenatide versus dulaglutide will be performed at the alpha level of 0.05.

#### **2.4.4.2.1 HbA1c < 7.0 % at Week 56 (yes/no)**

Proportions of participants achieving the HbA1c target value of <7.0% at Week 56 will be compared between each efpeglenatide dose versus dulaglutide using a Cochran-Mantel-Haenszel (CMH) test stratified by randomization stratum of Screening HbA1c (<8.0, ≥8.0%) and Visit 3 (Baseline, Day 1) BMI (<30, ≥30 kg/m^2) in the ITT population. For categorial secondary endpoint in which HbA1c is assessed at Week 56, all HbA1c values at Week 56 will be used to determine whether a participant is a responder (HbA1c <7.0%) or not, even if they are measured after IMP discontinuation or introduction of rescue therapy. Participants with missing HbA1c data at Week 56 will be considered not achieving HbA1c < 7.0%. The nominal p-value from the CMH test will be presented. No rounding for HbA1c will be done.

#### **2.4.4.2.2 Changes in FPG from Baseline to Week 56 and in body weight from baseline to Week 56**

Changes in FPG from baseline to Week 56 and in body weight to Week 56 will each be analyzed using the same ANCOVA model with missing values imputed by MI analysis method as the method used for the primary efficacy endpoint analysis. Differences between treatment groups and CIs will be estimated by this method. The least squares (LS) means, standard errors of LS means within each treatment group and the adjusted mean and associated two-sided 95% CI of the difference between efpeglenatide 4, 6 mg and 1.5 mg dulaglutide group will be presented.

Summary statistics at protocol scheduled visits and for the last on-treatment value will also be provided for FPG and body weight.

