##### **Primary Analysis:**

The statistical analysis for the primary endpoint is described below.

The Baseline value is defined in [Section 2.1.1](#).

Analysis of the primary efficacy endpoint (change from Baseline to Week 56 in HbA1c) will be performed using the ITT population, using HbA1c measurements obtained during the study, including those obtained after IMP discontinuation or introduction of rescue therapy.

The primary efficacy endpoint of change in HbA1c from Baseline to Week 56 will be analyzed with missing values imputed by BOCF-like MI method for both efpeglenatide and dulaglutide groups, under the MNAR framework:

- For participants with missing HbA1c values at Week 56, the missing values will be imputed using a random draw from a normal distribution with mean equal to their Baseline HbA1c and the standard deviation equal to the pooled standard deviation calculated from the square root of the mean square error estimated from a regression model with Baseline HbA1c as the dependent variable and randomization strata and treatment as the covariates.

In this analysis, missing endpoint values will be imputed 10 000 times to generate 10 000 data sets with complete data. Each of the complete datasets after the imputation will be analyzed by the ANCOVA model with the treatment groups (efpeglenatide 4 or 6 mg, dulaglutide 1.5 mg), randomization stratum of screening HbA1c ( $<8.0$ ,  $\geq 8.0\%$ ), Visit 3 (Day 1) BMI ( $<30$  and

$\geq 30 \text{ kg/m}^2$ ), and geographical region (North America, Eastern Europe (including Hungary and Poland)) as fixed effects, and baseline HbA1c value as a covariate.

In case a baseline value needed for multiple imputations is missing, it will be imputed by the population mean at Baseline.

SAS pseudo-codes are provided in [Appendix A](#).

Results from each complete dataset will be combined to provide the adjusted mean change in HbA1c from baseline to Week 56 (regardless of treatment discontinuation or initiation of rescue therapy) for each treatment group, as well as the between-group difference (comparing each efpeglenatide group versus dulaglutide group) and the 95% CI for the difference. This will be implemented using MIANALYZE procedure in SAS. If the UB of the 2-sided 95% CI for the adjusted mean difference (efpeglenatide versus dulaglutide) in HbA1c change from baseline to Week 56 is  $\leq 0.3\%$ , the noninferiority will be declared.

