#### **2.4.4.3 Multiplicity issues**

After noninferiority for the primary endpoint of change in HbA1c from Baseline to Week 56 has been established for both efpeglenatide 4 and 6 mg, the secondary endpoints will be tested in the prioritized order as follows:

1. Change from baseline to Week 56 in HbA1c for efpeglenatide 6 mg versus dulaglutide (Superiority)
2. Change from baseline to Week 56 in body weight for efpeglenatide 6 mg versus dulaglutide (Superiority)
3. HbA1c <7.0% at Week 56 for efpeglenatide 6 mg versus dulaglutide (yes/no) (Superiority)
4. Change from baseline to Week 56 in body weight for efpeglenatide 4 mg versus dulaglutide (Superiority)
5. Change from baseline to Week 56 in HbA1c for efpeglenatide 4 mg versus dulaglutide (Superiority)
6. HbA1c <7.0% at Week 56 for efpeglenatide 4 mg versus dulaglutide (yes/no) (Superiority)
7. Change from baseline to Week 56 in FPG for efpeglenatide 6 mg versus dulaglutide (Superiority)

8. Change from baseline to Week 56 in FPG for efpeglenatide 4 mg versus dulaglutide (Superiority)

The testing will stop as soon as an endpoint for an efpeglenatide dose is found to be not statistically significant at  $\alpha=0.05$  (2-sided). No multiplicity adjustment will be made on other secondary efficacy variables or the comparison of other efpeglenatide dose versus dulaglutide than those mentioned earlier in this section.

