**2.4.4.4.2 Change in HbA1c/body weight/FPG from baseline to Week 30**

Changes from Baseline in HbA1c to Week 30, in body weight to Weeks 30 and in FPG to Week 30 will each be analyzed by the same ANCOVA model with missing values imputed by MI method as described in section 2.4.4.1 the primary analysis.

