## **7 LIST OF APPENDICES**

Appendix A: Efficacy Analysis SAS pseudo code

Appendix B: Criteria for Potentially Significant Abnormalities

Appendix C Diagram for Identifying Missing Data due to COVID-19

Appendix D Schedule of Activities

## Appendix A Efficacy Analysis SAS pseudo code

### Primary Analysis missing data imputation:

- 1) Multiple imputations in participants who have missing HbA1c values at Week 56

**Step 1:** Perform regression to estimate pooled mean and standard deviation of non-missing baseline HbA1c measures

```
proc glm data=BaseHbA1c;
    class ARM HbA1c_strata BMI_strata;
    model base = ARM HbA1c_strata BMI_strata;
    ods output FitStatistics=basefit;
run;

proc sql noprint;
    select RootMSE, depmean
    into :std, mean
    from basefit;
quit;
```

**Step 2:** For participants with missing HbA1C values at week 56, simulate week 56 HbA1c 10000 times by random draw (with seed=14829) from a normal distribution with mean equal to baseline HbA1c and STD equal to the pooled STD from the regression model in Step 1. In case baseline HbA1c is missing, pooled mean is used as baseline HbA1c. For participants with non-missing HbA1C values at week 56, repeat the same record 10000 times (iteration 1 to 10000) to generate 10000 data sets.

```
data HbA1cW56Complete;
  set InputData;
  call streaminit(14829);
  do _imputation_ = 1 to 10000;
    if base = . then newbase = &mean; /* in case of missing baseline HbA1c measure, pooled mean is used as the
baseline HbA1c*/
    else newbase = base ;

    base_simu = rand ('normal', newbase, &std);

    if aval=. then do ;
      aval=base_simu ;
      msfl = 'Y'; /* Flag missing record for tipping analysis */
    end;

    chg_wk56 = aval - newbase ;

    output ;
  end;
run;
```

**Step 3:** Use ANCOVA and Rubin's formula to obtain the between-group difference and 95% CI.

```
proc mixed data=HbA1cW56Complete;
  class ARM HbA1c_strata BMI_strata region;
  model chg_wk56 = ARM HbA1c_strata BMI_strata region NEWBASE;
  by _Imputation_;
```

```
lsmeans ARM/ pdiff=control ('Dulaglutide 1.5 mg') cl;  
ods output LSMeans=lsmeans diffs=lsmeansdiff;  
run;  
  
proc mianalyze parms=lsmeansdiff;  
modeffects ARM;  
by ARM;  
ods output parameterestimates=miparm;  
run;
```

In this sample SAS® (version 9.4) code:

- BaseHbA1c contains one observation per participant in the ITT population with Baseline HbA1c value.

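### Missing Week 56 body weights are imputed with the between-person spread of baseline weight as noise, which widens the weight confidence interval and costs power at items 2 and 4 of the testing sequence if they are reached

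*SAP*

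**What the plan says.** SAP 2.4.4.2.2 (like protocol 9.4.1, Table 5) gives weight no imputation rule of its own. The change in weight is "analyzed using the same ANCOVA model with missing values imputed by MI analysis method as the method used for the primary efficacy endpoint analysis".

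That method is set out in SAP 2.4.4.1, Primary Analysis. A missing Week 56 value is drawn from a normal distribution centred on the participant's own baseline, with "standard deviation equal to the pooled standard deviation calculated from the square root of the mean square error estimated from a regression model" that has "Baseline HbA1c as the dependent variable and randomization strata and treatment as the covariates". Appendix A codes it in two lines. The SD is the root MSE from "model base = ARM HbA1c_strata BMI_strata", and the draw is "base_simu = rand ('normal', newbase, &std". Change is then the drawn value minus baseline, and the results are combined with Rubin's formula. No section sets another SD for weight, and Appendix A has no weight code.

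SAP 2.4.4.4.2 repeats the rule at Week 30: changes "in body weight to Weeks 30 and in FPG to Week 30 will each be analyzed by the same ANCOVA model" and the same imputation.

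In SAP 2.4.4.3, item 2 of the sequence is "Change from baseline to Week 56 in body weight for efpeglenatide 6 mg versus dulaglutide (Superiority"), and item 4 is the same test for 4 mg. "The testing will stop as soon as an endpoint for an efpeglenatide dose is found to be not statistically significant".

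**The concern.** Because the draw is centred on the participant's baseline and baseline is then subtracted, the imputed change is pure noise. Its SD is the residual spread of baseline between participants. For weight, the only size-related term in the regression is BMI below or at least 30 kg/m², so height and most of the BMI spread remain in that residual. The noise is independent of baseline, so the ANCOVA's baseline covariate cannot remove it.

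The noise is counted twice in Rubin's total variance: once in the residual variance of each completed data set, and once in the variance between imputations. Averaging over 10 000 imputations removes it from the estimate but not from the interval. Centring on baseline is the deliberate conservative step. The extra width is a by-product of moving an HbA1c rule to another scale.

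Item 2 gates items 3 to 8, so if it is reached and lost to imputation noise, all later claims are lost too. Even if the sequence stops earlier, the weight interval that 2.4.4.2.2 requires would be wider than the data warrant.

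**Working it through.** **The plan's own figure.** SAP 1.3 gives 91% power with 300 per arm, SD 1.1%, margin 0.3% and zero true difference. SE = 1.1 × √(2/300) = 0.0898, and Φ(0.3/0.0898 − 1.96) = 0.916, so the figure reproduces. Neither document gives a power, SD or effect for weight.

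**Why HbA1c escapes.** Entry is limited to 7.0 to 10.0% at screening (inclusion I 05). A uniform spread over that range has SD 3/√12 = 0.87. Pooled within the 8% strata it is √[(1/3)(1/12) + (2/3)(4/12)] = 0.50. Both are below the planned change SD of 1.1.

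**Assumed inputs for weight (not in the documents).** n = 300 per arm; change SD s_c = 5 kg; mean change μ = −3 kg; true difference d = 1.5 kg; draw SD s_b = 10 to 17 kg under the plan, against 5 kg for a draw on the change scale; missing share m = 2 to 15%.

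**Formulas.**
- Within-imputation variance: `W = (2/n)[(1−m)s_c² + m·s_b² + m(1−m)μ²]`
- Between-imputation variance: `B = (2/n)·m·s_b²`
- Reported SE: `√(W+B)`
- True sampling SD of the estimate: `V = √{(2/n)[(1−m)s_c² + m(1−m)μ²]}`
- Expected estimate: `(1−m)d`
- Power: `P(|estimate|/SE > 1.96)`

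**Worked at m = 10%.**
- s_b = 5: W = (2/300)(22.5 + 2.5 + 0.81) = 0.1721, B = 0.0167, SE = 0.434.
- s_b = 10: W = 0.2221, B = 0.0667, SE = 0.537.
- s_b = 17: W = 0.3481, B = 0.1927, SE = 0.735.
- V = 0.394 and the expected estimate is 1.35 kg in all three cases.

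The 95% half-width is 1.05 to 1.44 kg under the plan against 0.85 kg. Power is Φ((1.35 − 1.05)/0.394) = 77% down to Φ((1.35 − 1.44)/0.394) = 41%, against 90%. Two-sided type I error is 0.8% down to 0.03%, against 3.1%.

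| Missing | SE ratio, plan / change-scale | Power under plan | Power, change-scale |
|---|---|---|---|
| 2% | 1.06–1.19 | 89–94% | 95% |
| 5% | 1.13–1.41 | 74–89% | 93% |
| 10% | 1.24–1.69 | 41–77% | 90% |
| 15% | 1.32–1.91 | 15–62% | 85% |

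**Other inputs.**
- With 200 per arm and 10% missing, power is 20 to 55% against 74%.
- At 10% missing and 300 per arm, a true difference of 1.0 kg gives 9 to 35% against 55%; 2.0 kg gives 82 to 97% against 99%; 2.5 kg gives 98 to 100% against about 100%.
- The SE ratio stays above 1 for change SDs of 4 to 7 kg.

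**Simulation of the full rule.** Three arms of 300, ANCOVA with strata, region and baseline weight, Rubin's rules with 40 imputations, 500 runs per cell. Assumed heights were 1.76 m (SD 0.07) and 1.62 m (SD 0.065), half each, with mean BMI 33. The plan's draw SD came out at 12.7 kg for BMI SD 3 and 15.6 kg for BMI SD 6. Power at 2/5/10/15% missing was:
- 12.7 kg: 93/85/66/47%, against 92/91/88/84% with the change-scale draw.
- 15.6 kg: 90/80/50/26%, against 94/92/88/83%.

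With no true difference, 10% missing and 15.6 kg (1500 runs), rejection was 0.07% under the plan against 3.3%. A separate simulation with change SD 6 kg, mean change −3.5 kg and a draw SD of about 15.7 kg gave 40% against 72% at 10% missing.

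**FPG.** With an assumed baseline SD of 2.0 to 2.8 and change SD of 2.4 mmol/L, the SE ratio is 0.96 to 1.04, so the concern is limited to weight.

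**The case against.** The mechanism is not in dispute; its size and the remedy are.

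- **Size depends on unstated inputs.** At a true difference of 2.5 kg the power loss nearly vanishes, and at 2% missing it is small. This stands as a limit on the power figures. It does not bias them one way, since the loss is larger at 1.0 kg, and the widening of the interval does not depend on the effect size.
- **The missing share may be low.** SAP 2.5.4 accepts unscheduled weights within 30 days of Day 392, the protocol keeps participants in follow-up after they stop treatment, and the mITT definition drops those cut off earlier by termination. But mITT keeps participants who left the study before termination, and SAP 2.4.4 and 2.4.4.1 still name ITT. The share is unknown, not negligible by design.
- **Item 2 may never be tested.** It needs both noninferiority results and HbA1c superiority of 6 mg, in a trial sized for a zero HbA1c difference. True, which is why the power loss is stated as conditional. The reported interval is affected either way.
- **No false claim can result.** Correct: the error is conservative, and observed-case summaries are also reported.
- **A late change that narrows the interval favours the sponsor.** SAP version 2 is dated 02-Oct-2020, after termination on 9 September 2020, and the trial is open-label for drug. This is the most serious objection. It is met if the change is made before lock without arm-level weight results and is logged, and because the test remains slightly conservative afterwards.

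**Conclusion.** The concern holds and should be fixed. Read literally, the SAP gives body weight an imputation SD that measures differences between people, not one person's change. The direction is certain whenever the residual baseline weight SD exceeds the SD of change. The amount rests on assumed values: at 5 to 10% missing, the weight standard error is about 13 to 69% larger than with a change-scale draw. At a 1.5 kg difference, item 2 loses roughly 4 to 49 percentage points of power if it is reached (93 − 89 at the low end, 90 − 41 at the high end). The estimate is unchanged and type I error falls below nominal, so this is a loss of precision and power, not a threat to validity. The primary endpoint and FPG are not materially affected.

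**What to change.** Add to SAP 2.4.4.2.2, with a cross-reference in 2.4.4.4.2 for Week 30:

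> For body weight, a missing value is drawn with mean equal to the participant's own baseline weight and SD equal to the root MSE of the ANCOVA of the observed weight change at that visit on treatment, randomization strata, region and baseline weight.

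Settle this before database lock without sight of arm-level weight results, and record it in SAP 1.6, Table 1, as a departure from protocol 9.4.1. Leave the HbA1c and FPG rules as they are.

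The cost is one sentence, one cross-reference, one model line in Appendix A and one row in Table 1. Weight would no longer follow exactly the same draw rule as the primary endpoint, and the blind timing of the change has to be documented. Baseline centring is kept. The interval stays slightly conservative: reported SE over true sampling SD is 1.05, 1.10 and 1.16 at 5, 10 and 15% missing.

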#### **2.4.4.3 Multiplicity issues**

After noninferiority for the primary endpoint of change in HbA1c from Baseline to Week 56 has been established for both efpeglenatide 4 and 6 mg, the secondary endpoints will be tested in the prioritized order as follows:

1. Change from baseline to Week 56 in HbA1c for efpeglenatide 6 mg versus dulaglutide (Superiority)
2. Change from baseline to Week 56 in body weight for efpeglenatide 6 mg versus dulaglutide (Superiority)
3. HbA1c <7.0% at Week 56 for efpeglenatide 6 mg versus dulaglutide (yes/no) (Superiority)
4. Change from baseline to Week 56 in body weight for efpeglenatide 4 mg versus dulaglutide (Superiority)
5. Change from baseline to Week 56 in HbA1c for efpeglenatide 4 mg versus dulaglutide (Superiority)
6. HbA1c <7.0% at Week 56 for efpeglenatide 4 mg versus dulaglutide (yes/no) (Superiority)
7. Change from baseline to Week 56 in FPG for efpeglenatide 6 mg versus dulaglutide (Superiority)

8. Change from baseline to Week 56 in FPG for efpeglenatide 4 mg versus dulaglutide (Superiority)

The testing will stop as soon as an endpoint for an efpeglenatide dose is found to be not statistically significant at  $\alpha=0.05$  (2-sided). No multiplicity adjustment will be made on other secondary efficacy variables or the comparison of other efpeglenatide dose versus dulaglutide than those mentioned earlier in this section.

**2.4.4.4 Exploratory efficacy analysis**

The analysis of the exploratory endpoints will be descriptive in general with no formal testing, unless otherwise specified. Summary statistics at scheduled visits using OC will be provided by each treatment group. For the continuous exploratory endpoints, descriptive summary statistics will be provided, including the number of observations, mean, SD, SE, minimum, median, and maximum. Graphical presentations will also be provided as appropriate.

**2.4.4.4.1 HbA1c < 7.0 % at Week 30 (yes/no)**

Proportions of participants achieving HbA1c target values of <7.0% at Week 30 will be analyzed by same approach described in secondary endpoint: HbA1c < 7.0% at Week 56. Participants with missing HbA1c data at Week 30 will be considered not achieving HbA1c < 7.0%.

**2.4.4.4.2 Change in HbA1c/body weight/FPG from baseline to Week 30**

Changes from Baseline in HbA1c to Week 30, in body weight to Weeks 30 and in FPG to Week 30 will each be analyzed by the same ANCOVA model with missing values imputed by MI method as described in section 2.4.4.1 the primary analysis.

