### **2.3.1 Efficacy populations**

The efficacy analysis population will be the ITT population.

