#### **2.3.1.2 Modified Intent-to-treat population**

Due to the study terminated early by sponsor on September 9, 2020 (hereinafter referred to as “early termination”), the efficacy analyses will be performed in mITT population instead of ITT population originally planned. The mITT population is defined as,

- Participants who have completed the study treatment, or
- Participants who discontinued the study treatment AND completed/discontinued the study before the early termination, or
- Participants who discontinued treatment before early termination and discontinued the study due to early termination within 30 days of the target Week 56 visit (Day 392), or
- Participants who discontinued treatment due to early termination within 30 days of the target Week 56 visit (Day 392).

Participants will not be included in mITT if they discontinued study due to termination and discontinued study treatment (before or due to early termination) and had visits performed more than 30 days before the target Week 56 visit (Day 392).

By-visit summary will be provided for ITT population in addition for mITT population.

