## **2.4.4 Analyses of efficacy endpoints**

Efficacy analyses will be performed on the ITT population using efficacy assessment collected during the study, including those obtained after IMP discontinuation and/or introduction of rescue therapy, unless otherwise specified (see [Section 2.5.4](#)).

Due to COVID-19 pandemic, participants may not be able to maintain their regular clinical visits according to the study protocol, with the closure of facilities, safety concern for the participants to go to the sites, unavailability of the investigators for treating participants, interruption of transportation or other COVID-19 related reasons. Data missingness due to these reasons is likely to be missing at random. For a continuous endpoint, all observed data of participants within the same treatment group can be used for imputation in an MAR approach. Sensitivity analyses will be performed to take into consideration of the impact of COVID-19 if the number of participants with missing endpoint data due to COVID-19 is above the threshold as specified in the following sections.

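### The modelled Week 30 comparisons have no suitable analysis population: the mITT is tied to Day 392 alone, and the SAP elsewhere still says ITT

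*SAP*

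**What the plan says.** After the sponsor stopped the study on 9 September 2020, SAP 2.3.1.2 states that "the efficacy analyses will be performed in mITT population instead of ITT population originally planned". Each time criterion in the mITT refers to Week 56. Participants who left the study because of the termination are excluded if they "had visits performed more than 30 days before the target Week 56 visit (Day 392"). One group is kept whatever its timing: "Participants who discontinued the study treatment AND completed/discontinued the study before the early termination". No Week 30 version is defined. The same section adds that "By-visit summary will be provided for ITT population in addition for mITT population".

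Other sections still name ITT. SAP 2.3.1 says "The efficacy analysis population will be the ITT population". SAP 2.4.4 says "Efficacy analyses will be performed on the ITT population using efficacy assessment collected during the study", unless otherwise specified.

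Two sections make model- or test-based comparisons at Week 30:

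- SAP 2.4.4.4.2 covers "Changes from Baseline in HbA1c to Week 30, in body weight to Weeks 30 and in FPG to Week 30". It names no population and refers to SAP 2.4.4.1, which says ITT.
- SAP 2.4.4.4.1 follows the Week 56 responder analysis (SAP 2.4.4.2.1, also ITT) and adds that "Participants with missing HbA1c data at Week 30 will be considered not achieving HbA1c < 7.0"%.

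SAP 2.5.4 gives Week 30 its own target, Day 210. It accepts an unscheduled or end-of-treatment value within 30 days, or within 7 days for FPG.

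**The concern.** An analysis set for a Week 30 endpoint should depend on whether a participant could have contributed at Week 30. Neither available set does this.

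- **If SAP 2.3.1.2 governs**, someone still on treatment at Day 300 when the study stopped has a complete Week 30 assessment and is left out. Someone randomised at the same time who had already left treatment and study is kept. This costs precision and over-represents dropouts. Dropouts with no Week 30 value are imputed around baseline, so the estimates may shift as well.
- **If ITT governs**, nobody with a Week 30 value is lost. But participants whom the sponsor stopped before Week 30 are drawn around their baseline HbA1c, weight or FPG, or scored as non-responders. They neither failed treatment nor chose to leave.

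At stake are the adjusted Week 30 treatment differences and the responder comparison.

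**Working it through.** **The plan's own figure.** SAP 1.3 gives SD 1.1%, true difference 0, margin 0.3% and 300 per arm. The standard error of a difference is 1.1 × √(2/300) = 0.0898. Power is Φ(0.3/0.0898 − 1.96) = Φ(1.38) = 91.6%, against 91% stated. The figure reproduces. The documents give no figure for Week 30.

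**Who is affected under the mITT.** Inputs: termination on 9 September 2020 (SAP 2.3.1.2); Day 392, Day 210 and the windows (SAP 2.5.4). I count Day 1 as day one and assume that the last visit fell on the termination date.

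- The last excluded day is 392 − 31 = 361. Day 1 is 9 September 2020 minus 360 days = 15 September 2019. Day 362 is within 30 days of Day 392 and so inside the mITT.
- Day 210 reached: minus 209 days = 13 February 2020.
- For HbA1c and weight, a value from Day 180 can count: minus 179 days = 14 March 2020.
- For FPG, a value from Day 203 can count: minus 202 days = 20 February 2020.

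The core band is Days 210 to 361, or 361 − 210 + 1 = 152 days of possible enrolment.

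**Precision.** Let f be the share of the participants a Day 210 rule would keep who are excluded by the Day 392 rule. The documents do not give f. With equal shares across arms, the standard error grows by 1/√(1 − f). The absolute values below also assume that SD 1.1% holds at Week 30 and that a Day 210 rule would keep 300 per arm.

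| f (assumed) | n per arm | SE | 95% CI half-width | SE ratio |
|---|---|---|---|---|
| 0% | 300 | 0.090 | 0.176 | 1.00 |
| 10% | 270 | 0.095 | 0.186 | 1.05 |
| 20% | 240 | 0.100 | 0.197 | 1.12 |
| 30% | 210 | 0.107 | 0.210 | 1.20 |

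If some participants were stopped before Week 30, the absolute values are larger but the ratios are unchanged.

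**Over-representation of dropouts.** Suppose a share c of participants was randomised too late for the Day 392 rule, and a share d in every cohort had left treatment and study before termination. The mITT keeps (1 − c) + c·d, and dropouts make up d divided by that. With d = 10% and c = 30%, this is 0.10/(0.70 + 0.03) = 13.7% instead of 10%. With c = 10% it is 0.10/0.91 = 11.0%. Both inputs are assumptions.

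**The case against.** The strongest reply is that the mITT may not apply at Week 30 at all. Both Week 30 sections lead back to text that says ITT, and only SAP 2.3.1.2 says otherwise. This stands as a limit: a reader might infer that the SAP settles on the mITT for Week 30, and it does not. It does not rescue the plan, because full ITT treats participants stopped by the sponsor before Week 30 as unchanged from baseline or as failures.

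Second, SAP 2.4.4.4 makes these endpoints exploratory and in general descriptive, and none of the eight ranked hypotheses in SAP 2.4.4.3 is at Week 30. That is correct and limits the weight of the point.

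Third, a reader might infer that the exclusion has no reason behind it or that the Week 30 data are lost. Neither is supported. The termination is a stated reason for an mITT, and a single set keeps Week 30 and Week 56 on the same people. By-visit ITT summaries also remain, and a crude difference could be computed from them. But the SAP gives no reason for a Day 392 cut-off at Week 30, and observed-case summaries do not replace the adjusted estimates. SAP 1.6 shows that the same version that added the mITT also clarified the Week 30 and Week 56 windows, so the visit windows became visit-specific and the population did not.

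Fourth, a reader might take Week 30 to be the most complete efficacy time point after termination. The documents do not say so, and HbA1c is also measured at Week 12, which termination affects less.

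Last, the affected share is unknown and may be zero if enrolment closed before mid-September 2019. That stands, and is why the range starts at 0%.

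**Conclusion.** The point holds as a gap in the definition of the Week 30 population. The SAP contradicts itself on which set governs, and neither set suits Week 30. If the mITT governs, observed Week 30 values are left out of the modelled comparisons for participants with Day 1 from about 15 September 2019 to 13 February 2020, extending to about 14 March 2020 for HbA1c and weight and 20 February 2020 for FPG.

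The loss of precision cannot be derived from the documents. For an assumed 0% to 30% affected, the standard error is 0% to about 20% larger than necessary. The shift from over-represented dropouts is possible, and its size is likewise unknown. The consequence is confined to exploratory estimates: no confirmatory test, alpha allocation or Week 56 conclusion changes.

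**What to change.** In SAP 2.4.4.4.1 and 2.4.4.4.2, state that Week 30 endpoints use the mITT rules with Day 210 in place of Day 392 and with the window of SAP 2.5.4: 30 days for HbA1c and body weight, 7 days for FPG. A 30-day rule for FPG would admit participants whose FPG falls outside its window and would then be imputed around baseline.

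Word the rule as stopped by the termination no earlier than the window before Day 210. A literal swap of days in the inclusion criteria, which speak of being within 30 days of the target, could miss someone stopped at Day 300.

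Reconcile the ITT wording in SAP 2.3.1, 2.4.4, 2.4.4.1 and 2.4.4.2.1 with SAP 2.3.1.2, so that each efficacy analysis names one population.

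The cost is a few sentences and one or two extra population flags, with no new data. The downside is that Week 30 and Week 56 estimates would rest on slightly different sets of participants, which a table footnote can state.
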